imaging. See appendix 1 for the scan parameters. All assessments are performed by study members that are blinded for the treatment condition. The screening and baseline assessment will be performed during a single visit to the Amsterdam UMC, location VUmc.

Condition allocation and instructions

Following a positive screening for eligibility, a non-blinded study member will allocate the participant to either the CT or AC condition. Participants will be consecutively assigned to either the CT or AC condition on the basis of a randomization sequence. The randomization sequence is generated in Microsoft Excel by using computer-generated random numbers. We will use stratified randomization in which two strata will be generated according to education level. Vocational education level (or lower) defined as an education level of 5 or lower according to a Dutch classification system [56], which is comparable to 11 or less years of education [57]. High education level is defined as level 6 or 7 according to the Verhage classification system, which is comparable to 12 or more years of education.

A non-blinded study member will provide instructions to the participant concerning the log-in procedure for the training, the various training components, and the duration and frequency of training. After instructions, the participant will be asked to fill out a questionnaire concerning the patients' expectations and credibility regarding the intervention [58]. Participants will additionally receive a hand-out with instructions to take home.

Eight-week intervention period

After the baseline assessment, participants may directly start with the 8-week intervention. A detailed description of the CT and AC interventions is provided below. Compliance will be monitored automatically and will be checked weekly. During the intervention, patients will receive biweekly questionnaires to ensure compliance and check for questions and problems performing the intervention. Non-blinded study members will follow-up on potential problems by phone.

Post-intervention assessments

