 - change on latent underlying cognitive factors in the neuropsychological assessment at T1 and at follow-up (T2, T3, and T4). Participants will undergo an extensive assessment battery of frequently-used and validated neuropsychological tests (see Table 2). See [64] for standard outcome measures of the neuropsychological tests. We will extract latent cognitive traits at baseline and measure training-induced changes on these factors at follow-up (see Analyses for a detailed description);

- reduction of the risk of developing PD-MCI or PD-D at follow-up at one-year and two-year follow-up. We will classify participants at the follow-up visits into level II PD-MCI [65] and probable PD-D [66] according to the most recent diagnostic criteria;

3) Training-induced neural alterations will be measured with magnetic resonance imaging (MRI). Morphometric brain characteristics will be measured with standard measures (i.e. subcortical volume, cortical thickness, fractional anisotropy). We will measure functional connectivity by extracting independent components of simultaneously fluctuating blood-oxygen level dependent signals that represent resting-state brain networks. Brain network characteristics will be measured by standard topological measures (i.e. modularity, global and local efficiency, betweenness centrality, see [67, 68]).

Exploratory outcomes and covariates

For exploratory purposes, the following outcomes will be collected.

- Training-induced cognitive changes on individual neuropsychological tasks (see Table 2) will be assessed to increase comparability with other CT studies, and to increase replicability of the results in future research;
- Improvement on the individual CT games will be measured in order to compare potential component-specific transfer effects. Performance on the CT components are collected automatically by the BrainGymmer online training module;
- Alterations on psychiatric symptoms of anxiety, depression, apathy, and impulse control disorders, using the Parkinson anxiety scale, Beck depression inventory, Apathy scale, and Questionnaire for Impulsive-Compulsive Disorders in Parkinson's Disease – Rating Scale, respectively.

Additionally we will collect data on the following potential confounding factors:

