- Data on physical activity at each visit will be measured by the New Zealand Physical Activity Questionnaire – Short Form, a structured interview on mild, moderate and vigorous physical activity, as physical activity is known to positively influence cognitive function and potentially provide a neuroprotective effect.[69, 70];
- We will rate motor symptom severity by the Unified Parkinson's Disease – Rating Scale part III and assess disease stage by the modified Hoehn & Yahr stage [71];
- Medication usage data are collected and transformed into a 'levodopa equivalent daily dosage' [33]. Dopamine replacement therapy may influence cognitive functions [72, 73];
- Intervention compliance will automatically be monitored by the training module. We will calculate total compliance as the proportion of completed training games out of 24 total sessions: $[N_{\text{completed}} / N_{\text{total}}] \times 100\%$, in which N_{total} is 13 games x 24 sessions in the CT

condition, and 3 games x 24 sessions in the AC condition. We define non-compliance as a completion rate lower than 75%, in accordance with Petrelli and colleagues [74].

ANALYSIS PLAN

Data-analyses will be performed on the Modified-Intention-To-Treat population, which comprises the compliant participants that underwent at least 75% of the intervention and at least one post-training assessment. We will compare the baseline characteristics of this sample to the Intention-to-Treat population (all randomized subjects). Secondary Per Protocol-analyses will be performed comprising the population that underwent the complete study protocol. Analyses will be performed with IBM SPSS version 22 (Armonk, NY, USA) and in R [75]. We will employ a statistical threshold of $\alpha = .05$.

The primary outcome will be analyzed using a multivariate mixed-model analysis using the accuracy on the five separate task-loadings (S1-S5) of the ToL at post-training visit (T1) as dependent measures, the training condition (CT vs. AC) as independent measure and baseline score of the outcome measures as covariates. We will construct a separate adjusted model with age, sex and years of education as additional covariates of no-interest. No imputation of missing values will be performed as this is not needed in linear mixed models.

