The secondary outcome measures will also be analyzed with linear mixed-models with baseline score of the outcome measures as covariates. Subjective cognitive dysfunction will be modeled with the total score of the PD-CFRS (both self-report and caregiver) and the CFQ a) at post-training (T1) and b) at all follow-up assessments (T2, T3 and T4) as dependent variables. We will perform a factor analysis on all neuropsychological assessment outcomes (see Table 2) at baseline using a factor analysis with regularized maximum likelihood estimation to produce latent cognitive traits. We will compute baseline trait scores (i.e. factor scores), and compute trait scores at follow-up measurements based on the baseline factor analysis. The effect of CT on cognitive functions will be assessed with a multivariate mixed-model comparable to the above, using the trait scores as dependent variables. The effect of CT relative to AC on neuropsychiatric symptoms will be analyzed using similar multivariate mixed-models with as dependent variables the Beck Depression Inventory, the Parkinson Anxiety Scale, the Apathy Scale and the Questionnaire for Impulsive-Compulsive Disorders in Parkinson's Disease – Rating Scale. Covariates will be added to the regression model based on a change-in-estimate method if there is a change of $\geq 10\%$ of the regression coefficient for the intervention variable.

In order to analyze between-group differences in conversion to PD-MCI or PD-D, we will first classify patients at baseline, T3 and T4 as having normal cognition, PD-MCI or PD-D. We define conversion 'down' as conversion to a milder cognitive dysfunction classification, no conversion as classification in the same category at a later assessment visit and conversion

'up' as conversion to a worse cognitive function classification. We will assess the association between the intervention and conversion rate with a Fisher's exact test. Odds ratios and confidence intervals of the conversion 'down' and no conversion groups versus the conversion 'up' group will be computed as a measure of effect size.

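### The 10% change-in-estimate rule leaves the covariates of the neuropsychiatric (and possibly secondary) models to the data; one named baseline-only set would be a cheap improvement

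*Combined protocol and SAP*

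**What the plan says.** The paragraph of the Analysis Plan on secondary outcomes sets linear mixed models adjusted for the baseline score. It covers subjective complaints, then latent cognitive traits, then neuropsychiatric symptoms, for which it plans "similar multivariate mixed-models with as dependent variables the Beck Depression Inventory, the Parkinson Anxiety Scale, the Apathy Scale" and the impulse-control scale. The paragraph ends with the rule: "Covariates will be added to the regression model based on a change-in-estimate method if there is a change of" 10% or more "of the regression coefficient for the intervention variable". It gives no candidate list, measurement time or order of entry, and does not say what happens if the four scales call for different covariates.

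The section on exploratory outcomes and covariates introduces the neuropsychiatric outcomes with "For exploratory purposes, the following outcomes will be collected". It then lists possible confounders: physical activity at each visit, motor severity and disease stage, levodopa-equivalent dose, and intervention compliance. The rule does not refer to this list.

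Other analyses are handled differently. For the primary outcome: "We will construct a separate adjusted model with age, sex and years of education as additional covariates of no-interest". For conversion to PD-MCI or PD-D: "We will assess the association between the intervention and conversion rate with a" Fisher's exact test, which has no covariates.

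**The concern.** Change-in-estimate is a screen for confounding. Under randomisation a baseline covariate can shift the treatment coefficient only through chance imbalance combined with its association with the outcome. The 10% is taken relative to the treatment estimate, so the bar is lowest when that estimate is near zero. The same covariate, with the same prognostic value, is kept in one realisation of the trial and dropped in another.

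Three things are at stake. Two analysts following the text could fit different models. A multivariate model with four scales could carry different covariates for each. And the rule as written does not bar variables measured after randomisation. Compliance is one by definition, and physical activity at follow-up visits is another. Adjusting for such a variable when it differs by arm could bias the treatment effect.

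**Working it through.** **1. The plan's own figure.** The plan gives no number for this rule. The nearest figure is the sample size of 112 (Sample size section: f = .12, r about .6, repeated-measures ANOVA). Noncentrality = f² × N × 2/(1 − r) = .0144 × 112 × 2/.4 = 8.06. On F(1, 110) at alpha .05 this gives 80.4% power, so 112 is reproduced. Read as an interaction effect, f = .12 is a difference in change of 4 × .12 = 0.48 SD, whereas the cited Hedges g is 0.23. Both effect sizes are used below.

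**2. Setting.** Analysed N = 140 × 0.9 = 126 (the plan's 10% drop-out), 1:1, r = .6. Residual variance = 1 − .36 = .64. SE = 2 × √.64/√126 = 0.143. Power at 0.23 SD with baseline score only is about Φ(0.23/0.143 − 1.96) = 36%.

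**3. What moves the coefficient.** The change on adding a covariate equals, apart from sign, its fitted slope times its imbalance between arms. For a standardised covariate unrelated to outcome:
- SE of the imbalance = 2/√126 = 0.178, and SE of the slope = 0.8/√126 = 0.071. The typical product is 0.178 × 0.071 = 0.013.
- The threshold is 0.1 × 0.48 = 0.048 for an estimate of 0.48, and 0.023 for an estimate of 0.23.
- With no true effect the estimate is itself of the order of its SE, so the threshold is about 0.1 × 0.143 = 0.014, the same size as noise.

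**4. Simulated selection** (single-visit ANCOVA, three or four baseline candidates).
- A pure-noise candidate enters in about 35% of trials with no effect, 15-16% at 0.23 SD, 4% at 0.40 SD and 2% at 0.48 SD.
- At 0.23 SD a prognostic candidate is omitted in 60-65%, 47-54% or 41-46% of trials when the candidates jointly explain .1, .2 or .3 of residual variance (R², assumed). So the rule favours prognostic covariates but often misses them.
- If the rule is run scale by scale, all four scales receive the same set in only 10-42% of trials at 0.23 SD.

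**5. Simulated power at 0.23 SD, %** (age, sex, years of education as candidates).

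| R² (assumed) | Baseline score only | 10% rule | Fixed set | Fixed minus rule |
|---|---|---|---|---|
| 0 | 35-36 | 36 | 34-35 | −1 |
| .1 | 35-37 | 36-38 | 37-39 | +1 to +2 |
| .2 | 35 | 37-39 | 41-42 | +3 to +4 |
| .3 | 35-36 | 41-42 | 46-48 | +5 to +6 |

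With six candidates the gain is smaller: −1.8 points at R² 0, −0.4 at .05, +0.3 at .10 and +3.0 at .20. At 0.48 SD with six candidates the difference runs from −1.4 (R² 0) to +1.8 (R² .20).

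**6. Validity and movement of the estimate.** Under the rule, type I error is 3.4-5.4%, the mean estimate is 0.229-0.236 for a true 0.23, and coverage is 94.5-96.6%. At 0.23 SD the rule's estimate and the fixed-set estimate differ by a median below 0.01 SD (90th percentile about 0.03). The significance verdict differs in 3-6% of trials for R² up to .2.

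**7. Post-randomisation variables.** Compliance is counted against 13 × 24 = 312 games in the training arm and 3 × 24 = 72 in the control arm, so its distribution could differ by arm. The documents give no data from which to size the resulting bias.

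**The case against.** The strongest defence is that the rule does little harm. A numeric criterion is stated in advance, the baseline score is already fixed in these models, and the answer barely moves when the chosen set does. That stands for baseline candidates, and it is why severity is low. It is also fair that the power gain rests on an assumed R², which the documents do not supply for depression, anxiety, apathy or impulse-control scores. And age, sex and education are not on the protocol's own list of possible confounders. If that set has no prognostic value and the listed disease factors do, fixing it loses 2-3 points to the rule run on those factors.

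Several stronger readings are tempting, but the documents do not support them:
- *The rule inflates type I error or biases the effect.* Not with baseline candidates applied mechanically (step 6). Trying several lists or orders of entry was not simulated.
- *Covariates are picked by chance alone.* Selection also follows prognostic strength (step 4).
- *Each scale will get its own set.* The text speaks of one model and one coefficient, so this is left open rather than planned.
- *Compliance will be adjusted for.* The rule is not tied to the confounder list. The text permits it but does not say it.
- *The education stratification factor will be left out.* The protocol says "We will use stratified randomization in which two strata will be generated according to education level" and "The randomization sequence is generated in Microsoft Excel by using computer-generated random numbers", but not whether the sequence is blocked, and education is not named as a candidate for the rule.
- *The primary or conversion results are affected.* Both are specified separately.

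What the defence does not answer is that the candidates, their timing and the rule's scope are unstated.

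**Conclusion.** The point holds as a cheap improvement of low severity. The rule certainly reaches the exploratory neuropsychiatric models. Its reach to subjective complaints and latent traits is inferred only from its position at the end of their paragraph. The main reasons to replace it are a model that another analyst can reproduce and the exclusion of post-randomisation variables, whose possible bias cannot be sized from the documents. Power is a secondary and conditional benefit: about +1 to +6 points at 0.23 SD for a set explaining 10-30% of residual variance, and about −1 point for one explaining none.

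These figures rest on assumed covariate strengths, a two-sided test, 10% loss at random, and a single-visit ANCOVA in place of the planned multivariate mixed model. The chance-imbalance argument applies strictly to all randomised participants. The analysis population excludes those below 75% compliance, so some imbalance could be systematic, which is a further reason to fix the set in advance.

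**What to change.** For the secondary and exploratory models only, leaving the primary analysis as it is:
- Replace the 10% rule with one named baseline-only set, used for every dependent variable: baseline score, age, sex and years of education, coded as in the primary adjusted model.
- Decide in advance whether named baseline disease factors, for example UPDRS-III, are included. Do not leave them optional.
- State that compliance, and activity or medication measured after randomisation, do not enter the effect model.
- If the 10% rule is wanted, keep it as a labelled sensitivity analysis with its candidates listed.

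The cost is SAP wording, since these variables are already collected. The statistical downside at 0.23 SD is about 1 point of power if the set is not prognostic, or 1-2 points with disease factors added. If only a non-prognostic age, sex and education set is fixed, the loss is 2-3 points against the rule run on prognostic listed factors. That is a reason to settle the disease factors explicitly.

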The study objectives of the COGTIPS study involve assessing an easily-accessible, home-based cognitive function training in individuals with mild subjective cognitive complaints in PD. Our *primary objective* is to assess the efficacy of an online CT program (compared to an active control condition) on executive functions. Our *secondary objectives* are to evaluate CT compared with an active control condition (AC) on 1) the efficacy on relieving subjective cognitive complaints; 2) the durability of the effect after six months, one year and two years; 3) the rate of conversion to PD-MCI and PD-D after one year and two years; 4) the effect on

brain network efficiency and connectivity. Furthermore, we aim to identify baseline brain network characteristics that predict treatment outcome.

Based on previous literature on CT in PD and other neurodegenerative diseases, we hypothesize that compared with an active control condition 1) CT alleviates cognitive –mainly executive– dysfunction in PD patients, 2) CT relieves subjective cognitive complaints in daily-life, 3) the CT effect endures for up to two years after finishing the intervention, and reduces the risk of conversion to PD-MCI and PD-D, and 4) CT improves brain network efficiency and connectivity.

Study design and setting

COGTIPS is a monocenter phase-III randomized controlled trial that will enroll one-hundred-and-forty (140) PD patients. To assess the superiority of the online CT compared with an AC, participants are randomly appointed to either of the conditions in a 1:1 fashion (70 versus 70). Eighty participants (i.e. 40 in each condition) will undergo pre- and post-training neuroimaging to assess CT-specific effects on functional and structural connectivity. This study was approved by the VU University Medical Center Medical Ethical Committee and this protocol is reported in accordance with SPIRIT guidelines [49].

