A space occupying lesion	Assessment by radiologist	-
Significant vascular abnormalities	Assessment by radiologist	Fazekas > 1
Severe claustrophobia	MRI safety screening	Positive screening
Presence of metal in the body (e.g. pacemaker, neurostimulator)	questionnaire	
Pregnancy		
Difficulty with, or shortness of breath during 60 minutes of lying still		

Participant timeline

Figure 1 shows a global overview of the time schedule. A detailed description of the participant visits and assessments is shown in Table 2.

[figure not shown]

Figure 1 Global overview of the COGTIPS time schedule.

Pre-screening, screening and baseline assessment

PD patients that have shown interest in participating in COGTIPS will first undergo pre-screening for which they are required to sign informed consent and send this back by mail or E-mail. Pre-screening consists of a self-administered cognitive screening and questionnaires that are filled out at home (i.e. Self-administered Gerocognitive Examination [50]), and a phone interview. Patients are asked whether they are interested in participating in the subgroup that will undergo neuroimaging and if so, are screened for contraindications. After positive pre-screening, eligible patients are invited for an intake measurement.

At intake, patients will sign informed consent for participation in COGTIPS. They first undergo face-to-face screening of cognitive dysfunction by the Montreal Cognitive Assessment [51, 52], motor impairment by the Unified Parkinson's Disease – Rating Scale part III [53], psychotic symptoms by the Schedule for Assessment of Positive Symptoms – PD [54], depressive symptoms by the Beck Depression Inventory [55] and impulse control disorders (ICDs) by an ICD criteria interview. Eligible patients will undergo the baseline assessment ('T0') which comprises an extensive neuropsychological assessment, structured interviews and questionnaires. A sub-population will undergo magnetic resonance imaging. Neuroimaging data will be acquired at the Amsterdam UMC, location VUmc, on a Discovery* MR750 3.0T MRI scanner (General Electric, Milwaukee) with a 32-channel head coil. We will obtain structural imaging (i.e. T1 and diffusion tensor imaging) and functional resting-state

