We will perform Fisher's exact tests to verify if the demographic and clinical characteristics of the MRI subsample are similar to those of the full study sample. Functional MRI and diffusion tensor imaging data will be (pre)processed and analyzed with Statistical Parametric Mapping (SPM) software, FMRIB Software Library (FSL) and in-house Matlab (The MathWorks, Inc, Natick, MA, USA), scripts in combination with open-source toolboxes for (dynamic) network analysis [67, 68] to study the effects of cognitive training on the functional and structural brain network, respectively. We will also employ typical independent component analysis in combination with dual regression for resting-state functional connectivity and morphometric (e.g. cortical thickness) analysis on T1-weighted structural MRI to study within and between group-effects of our intervention. Moreover, to establish treatment response at the individual level, Multivariate Pattern classification ('machine learning') analyses will be performed to identify predictive markers (clinical, neuropsychological and neuroimaging) to be able to predict (in future patients) who is most likely to benefit from cognitive training.

Sample size

The sample size calculation is performed on the basis of a previous meta-analysis on the effects of CT on cognitive function [22]. This study showed an effect size of Hedges $g = .23$ (i.e. $f = .12$), based on the effect of CT on improving *global* cognitive function. The sample size needed to detect this effect is 112, based on a repeated-measures analysis of variance, corrected for a moderate correlation between pre- and post-treatment measures (i.e. $r \approx .6$). This sample size estimation also provides a good indicator for the power of our multivariate mixed-model regression analysis with adjustment for baseline measures.

To ensure adequate power for the secondary study parameters, i.e. the development of PD-MCI and PD-D at one and two years follow-up, with an $\alpha = .05$ and $\beta = .8$, and based on a small drop-out ($\sim 10\%$) given the home-based, easily-accessible training, we will include 140 participants.

References

1. Jankovic J: **Parkinson's disease: clinical features and diagnosis.** *Journal of neurology, neurosurgery, and psychiatry* 2008, **79**:368-376.

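### The MRI representativeness check compares the 80 scanned participants with the 140 that include them, which strongly reduces its power to show selection

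*Combined protocol and SAP*

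**What the plan says.** In the ANALYSIS PLAN, the paragraph on the imaging analyses opens: "We will perform Fisher's exact tests to verify if the demographic and clinical characteristics of the MRI subsample are similar". The comparator is named in the same sentence: "demographic and clinical characteristics of the MRI subsample are similar to those of the full study sample". No other test, effect measure or similarity margin is given for this check. The general significance level is .05 (ANALYSIS PLAN, first paragraph); sidedness is not stated.

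Study design and setting fixes the sizes. The trial is a "randomized controlled trial that will enroll one-hundred-and-forty (140) PD patients", and "Eighty participants (i.e. 40 in each condition) will undergo pre- and post-training neuroimaging". The scanned group is therefore part of the 140, and 60 participants are not scanned.

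The scanned group is not a random subset. Under Pre-screening, screening and baseline assessment: "Patients are asked whether they are interested in participating in the subgroup that will undergo neuroimaging and if so, are screened for contraindications". Table 1 adds exclusions that apply only to imaging, among them "Significant vascular abnormalities", metal in the body, severe claustrophobia and difficulty lying still for an hour.

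**The concern.** Fisher's exact test compares two independent groups. If the second group is the whole trial, 80/140 = 57% of it is the first group, and part of the comparison is of people with themselves. The error runs in the unhelpful direction: overlap pulls the two percentages together, and the test does not know that they are correlated.

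The check is there to reveal selection. Volunteering, the contraindication screen and the extra exclusions make some selection plausible, and brain network effects are a stated secondary objective. A check that leans towards similarity may give more reassurance than it has earned about whom the imaging results describe.

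The second issue is the choice of test. Fisher's exact test is for categorical data. UPDRS-III, levodopa equivalent daily dosage and MoCA are collected as scores or continuous quantities, and the plan does not say how such variables enter the check.

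**Working it through.** The documents give no power or detectable difference for this check, so there is no planned figure to reproduce first.

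**Inputs.** MRI n = 80 and full sample n = 140 (Study design and setting), so non-MRI n = 140 − 80 = 60. Significance level .05 (ANALYSIS PLAN), taken as two-sided. The true proportions in the MRI group (pM) and the non-MRI group (pR) are assumptions, shown as a range.

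**Step 1: the difference shrinks.** The full-sample proportion is (80·pM + 60·pR)/140. Hence

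pM − pFull = (60/140)(pM − pR) = 0.43 (pM − pR).

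A 20-point difference between scanned and unscanned participants appears as 8.6 points.

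**Step 2: the test uses the wrong standard error.** In units of √[p(1 − p)]:

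- assumed for independent groups of 80 and 140: √(1/80 + 1/140) = 0.140
- true value for the overlapping difference: (60/140)·√(1/80 + 1/60) = 0.43 × 0.171 = 0.073

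The z statistic is therefore 0.073/0.140 = 0.52 of its proper value. To reach 1.96, the proper z must be about 1.96/0.522 = 3.75, so the real two-sided error rate is about 0.0002 in place of .05.

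**Step 3: exact rejection rates.** Every outcome of two independent binomials (n = 80 and n = 60) was enumerated, and the two-sided Fisher test at .05 was applied to the overlapping table (80 versus 140) and to the disjoint table (80 versus 60). The rates are per binary characteristic.

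| Assumed true MRI / non-MRI | As written (80 vs 140) | Disjoint (80 vs 60) |
|---|---|---|
| 50% / 50% | 0.01% | 3.9% |
| 45% / 55% | 0.4% | 19% |
| 40% / 60% | 7% | 61% |
| 40% / 65% | 18% | 82% |
| 35% / 65% | 39% | 93% |
| 30% / 70% | 84% | 99.7% |
| 25% / 75% | 99% | 100% |

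Around 50%, power of 80% needs a true difference of about 39 points as written and about 25 points with disjoint groups. For less common traits the overlap costs less in absolute size, but the pattern is the same: 10% versus 30% is flagged 26% of the time as written and 84% when disjoint.

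**Step 4: one observed table.** Take 48/80 MRI (60%) and 24/60 non-MRI (40%). The full sample is 72/140 (51.4%). Fisher's test gives p = 0.26 for 48/80 versus 72/140 and p = 0.026 for 48/80 versus 24/60.

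**Step 5: continuous characteristics.** By normal approximation with the same factor of 0.52, a shift of 0.5 SD between scanned and unscanned participants is detected 20% of the time with overlapping groups and 83% with disjoint ones; for 0.8 SD the figures are 82% and 99.7%.

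**The case against.** The strongest reply is that the wording is loose. Anyone who cross-tabulates a characteristic by scanned yes/no gets 80 versus 60 without trying; the 80-versus-140 table requires counting people twice. The plan uses the same part-against-whole phrasing when it compares the modified intention-to-treat sample with all randomised subjects, so this may simply be how the authors write. That reading is possible, but the text does not state it, and the same edit settles it.

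It can also be said that this is one descriptive check, that the imaging exclusions are openly listed, that nothing in the documents shows selection of 25 or 30 points, and that the disjoint comparison is itself weak for small differences (19% at 45% versus 55%). All of this stands. It limits the weight of the point but leaves the planned comparison defective as written.

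Three stronger readings are tempting and are not supported:

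- *A reader might infer that the check will almost always report similarity, however strong the selection.* The figures contradict this: detection as written reaches 84% at 30% versus 70% and 99% at 25% versus 75%. Testing several characteristics also raises the chance that at least one is flagged.
- *A reader might infer that the plan relies on this check to carry the imaging results over to the whole trial.* No such step, decision rule or adjustment is written down.
- *A reader might infer that Fisher's test will be applied to every characteristic, including raw continuous scores.* The plan names no variables and is silent on continuous ones. That is a gap in specification.

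**Conclusion.** The point holds for the text as written. Comparing the 80 with the 140 that contain them breaks the independence assumption, reduces the visible difference to 43% of the relevant one, and leaves a test with a real error rate near 0.01–0.02% and strongly reduced power for differences up to about 30 points around 50%. Very large selection would still be detected.

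The sizes rest on the planned numbers of 80 and 60, a two-sided .05 level, one binary characteristic at a time and assumed true proportions. They do not apply if the authors meant the other 60 participants; in that case the comparator needs to be stated.

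A further weakness remains under either reading: p > .05 is not evidence of similarity. Even 80 versus 60 misses a 40% versus 60% difference 39% of the time.

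The primary efficacy analysis and the comparison of training with control within the MRI group are not affected. This is a correction worth making to a secondary check.

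**What to change.** Replace the sentence in the ANALYSIS PLAN with one that does the following:

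- compares MRI participants with non-MRI participants (about 80 versus 60) and says so explicitly;
- lists the characteristics to be compared;
- reports standardised differences with 95% confidence intervals as the main evidence;
- uses Fisher's exact test for categorical characteristics and t or Mann-Whitney tests for continuous or ordinal ones, as support only;
- states that similarity will not be concluded from p > .05.

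The cost is a short edit to the analysis plan. No new data are needed. The small downside is that the check will more often show a difference that has to be discussed.
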